# 5.0 Study Procedures

# 5.1 Study Design

**Overview:** The study is a prospective double-blind placebo-controlled RCT to evaluate the efficacy of prazosin for prophylactic treatment of frequent persistent HAs following blast and/or impact mTBI in a convenience sample of male and female SMs and Veterans aged 18 and older who have a history of mTBI with chronic PTHAs and who meet inclusion/exclusion criteria as described further below. We anticipate enrollment of 228 participants to achieve 160 randomized -- an average of approximately 4-5 participants randomized per month divided approximately equally across the 2 sites.

All study procedures are investigational; none are standard of care. The total trial length is up to 24 weeks, including a 5-week Preliminary Screening Period during which the participant will keep a HA log, eligibility for randomization will be determined, and baseline data (including 1 week of sleep/activity monitoring using actigraphy and keeping a sleep log) will be collected; a 5-7week Titration Period, during which optimal dose will be determined; and a 12-week Steady-Dose Period, as detailed in section 5.5 below and in the schedule of study visits table.

Participants who remain eligible after the Preliminary Screening period will be randomly assigned 2:1 to prazosin or placebo and will then begin the study drug dose Titration Period. During the Titration Period, the dose of study drug will be gradually increased to a maximum dose of 5 mg each morning and 20 mg each evening or to the maximum tolerated dose. Once the maximum (or maximum tolerated) dose has been attained, the participant will continue on this dose for 12 weeks. Evaluations to be performed are described in section 5.5 below and on the Schedule of Study Visits table.

**Investigational Drug:** This study will be conducted using the drug, prazosin, which has been approved by the FDA for treatment of hypertension but is being used off-label for investigational purposes in this study. Prazosin and indistinguishable placebo will be obtained from commercial sources. Investigational pharmacists at each study site will procure the study drug. Study drug may be stored at room temperature. Unused drug will be disposed of by the investigational pharmacists once notification has been made by the PI that the study has been completed.

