Participants will begin keeping the HA log at the beginning of the Preliminary Screening period and will continue for the duration of the Preliminary Screening Period. If they are determined to be eligible to continue in the study (see below), they will continue keeping the HA log for the remainder of the study phases, including the Titration and Steady-Dose Periods. The Screening HA log data will be used to both confirm that participants are eligible to continue into the Titration Period of the study and to provide baseline data that will be used for comparison with data from the Steady-Dose Period to address the primary and secondary outcome measures.

Participants will be called for a brief telephone visit during weeks 1 and 3 of the screening period. The calls will answer any questions about the HA log keeping and encourage compliance. Medication and health changes will be queried.

At the end of 4 weeks of HA log keeping, the HA log will be reviewed at the Final Screening Visit to determine participant eligibility to continue in the study. Eligibility criteria include 8 or more HA days in the 4-week period of log keeping. A HA day is defined as a calendar day in which the participant had HAs that either 1) lasted for 4 or more hours and reached a pain intensity of moderate to severe at any point during the HA or 2) were of any severity or duration if the participant took a medication or other agent (e.g., caffeine) in an effort to stop or treat a headache. HA log entries must be recorded for at least 80% of the days, and there must be no exclusionary medication or supplement use. Vital signs (BP and HR) will be checked to ensure absence of orthostatic hypotension. Participants will be scheduled for the Baseline Visit, which will optimally occur 7 days later, but not more than 14 days later. During the interim week between the Preliminary Screening Period and the Baseline Visit, participants will

continue keeping the HA log and will undergo baseline sleep/activity monitoring with 7 days of actigraphy and keeping a sleep diary.

If it is found that a potential participant does not meet the inclusion criteria, follow-up care will be coordinated when needed with the appropriate clinic at the study site, either Madigan or VA Puget Sound.

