**Study Drug Titration Schedule** 

Steady-Dose Period Visits and Telephone Check: Regular clinic visits will be scheduled. Safety and efficacy visits will be scheduled at the completion of Steady-Dose weeks 1, 4, 8, and 12 to record any interval medical or medication changes, to monitor compliance, and to confirm that the HA Log is current. Participant safety will be assessed at each of these visits, as further detailed in the "Risk Management and Emergency Response" section above. Any adverse symptoms will be recorded, evaluated, and addressed, as appropriate, and safety measures (resting and standing BP and HR) will be performed. The Actiwatch, actigraphy instructions, and the sleep log will be issued to the participant inperson or will be shipped to the participant prior to the week 11 telephone check-in visit. Shipping will occur via trackable method such as Fed Ex or UPS.

At the end of Steady-Dose weeks 4, 8, and 12, in addition to safety assessments and monitoring, all secondary outcome measures will be repeated, as described in the schedule of study visits. At the 12-week visit, approximately 65 ml of blood will be collected from VA Puget Sound participants only for measurement of potential headache biomarkers. In the event of early termination, (see section 5.7 below), a termination visit will be scheduled whenever possible to complete all procedures usually performed at week 12.

Potential Exceptions to study schedule: If a participant delays titration for any reason (e.g., dose maintained and not increased due to temporary AE), up to two additional titration visits may take place

(extending the 5 week titration to 7 weeks). No dose increases may take place after starting the Steadydose Period.

Study visits windows are up to 6 days before or after each scheduled visit. Outcome rating visits may be done up to 14 days before or after the scheduled outcome rating visit. The screening process (consent visit through completion of all visit P1 procedures) may last as long as 6 weeks due to stabilization of medications and health conditions.

Additional visits (for example, additional titration visits or additional safety visits) may be required per study clinician's discretion. If additional visits are required, participants will be reimbursed as if it were a regular study visit.

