#### **Description of Study Measures:**

Structured Clinical Interview for DSM-5 (SCID-5):A semi-structured interview guide for making DSM-5 diagnoses. It is administered by a clinician or trained mental health professional that is familiar with the DSM-5 classification and diagnostic criteria.

Combat Experiences Scale (CES): The 18-item Combat Experiences Scale will be used to describe the degree of combat trauma exposure in the study sample. Scores range from 1-18. The Combat Experiences Scale has been utilized in many studies evaluating combat veteran samples and is relevant to any war zone setting from WWII to OIF/OEF/OND.

HA Log: A pre-printed form in a weekly calendar format used for self-report of the following, on a daily basis: HA pain severity (maximum for the day, rated as none [=0], mild [=1], moderate [=2], or severe [=3]), number of hours of mild, moderate or severe pain (to nearest ½ hour), any medications used in an attempt to treat the HA, including the name, amount, and whether it provided relief, , and a space for comments.

Migraine Disability Assessment Scale (MIDAS): A 5-item self-administered questionnaire used to quantify HA-related disability. The MIDAS queries the number of days of missed or substantially reduced activity caused by HA in the preceding 3 months, taking into account three domains: schoolwork/employment, household work or chores, and non-work activities (family, social, and leisure). Responses are summed and coded into one of four grades of disability ranging from little or no

disability to severe disability.

HA Impact Test-Short Form (HIT-6): A 6-item self-administered questionnaire measuring impact on "usual daily activities" including work, school, or social activities, pain intensity, fatigue, and desire to lie down, frustration, and difficulty with concentration in the preceding month. The HIT-6 has shown the ability to discriminate between severity levels and between migraine and other HA diagnoses.

PTSD Checklist (PCL-5): A 20-item self-report measure that assesses the DSM-5 symptoms of PTSD on a scale ranging from 0 ("not at all") to 4 ("Extremely")

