**Statistical Analysis:** We will use summary statistics and graphs (e.g., strip charts, box plots, bar charts, scatter plots) to compare subject demographics at baseline by assigned treatment group (prazosin vs. placebo), and to initially compare outcomes by treatment group. Analyses will follow the intent to treat (ITT) principle. We will use a linear mixed effects model for the analysis of the primary outcome: 4-week frequency of moderate or severe HAs (Hypothesis 1a). We will have 4-week measures at four times during the course of the study: at Baseline, and at three different time points post-randomization (after 4, 8, and 12 weeks of steady-dose study drug). The response (dependent) variable will be 4-week frequency of moderate or severe HAs, and the predictor (explanatory) variables will include treatment group, week and a treatment group by week interaction term, along with the covariates site, gender, baseline age, baseline PSQI, time since onset of PTHAs, and analgesic use. A significant treatment group by week interaction term will indicate a significant difference in change from baseline between treatment groups. Results will include p-values, confidence intervals for change from baseline within each group, the confidence interval for difference in change from baseline between the two groups, and effect sizes.

We will also use linear mixed effects models for the secondary outcomes for Hypothesis 1b, i.e., 4-week average of: HA severity, number of hours of moderate to severe HA, individual HA duration, frequency of migraine days, frequency of non-migraine days, and frequency of use of abortive/analgesic medications (all obtained from the HA log); and for degree of HA-related disability (MIDAS and HIT-6). As for the primary outcome, secondary outcomes obtained from the HA log and the HIT-6 will have observations at four time points during the course of the study: Baseline and after 4, 8, and 12 weeks of steady-dose study drug; MIDAS will have observations at Baseline and week 12. The response (dependent) variable will be the secondary outcome, and the predictor (explanatory) variables will be the same as for the primary outcome.

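### Is the primary headache outcome too loosely defined (unit, log windows, unlogged days) to be analysed as planned?

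*Combined protocol and SAP*

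**What the plan says.** Section 5.6 (Statistical Analysis) names the "primary outcome: 4-week frequency of moderate or severe HAs (Hypothesis 1a" and takes it as a 4-week measure at baseline and at the close of steady-dose weeks 4, 8 and 12. The log behind it is described in Section 5.5 (Description of Study Measures). Each day the participant enters "HA pain severity (maximum for the day, rated as none [=0], mild [=1], moderate [=2], or severe [=3", the hours spent at each severity, and medications taken.

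On timing, Section 5.1 describes the pre-treatment phase as "including a 5-week Preliminary Screening Period during which the participant will keep a HA log". Section 5.5 has the log reviewed after four weeks and names the screening log as the source of baseline data. It then schedules the Baseline Visit, "which will optimally occur 7 days later, but not more than 14 days later"; in that interval participants "continue keeping the HA log and will undergo baseline sleep/activity monitoring". For follow-up, "Outcome rating visits may be done up to 14 days before or after the scheduled outcome rating visit".

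On completeness, "HA log entries must be recorded for at least 80% of the days", but this is a screening requirement. The headache day used for eligibility also differs from the primary measure: it includes headaches that "were of any severity or duration if the participant took a medication or other agent".

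**The concern.** Read alone, the outcome sentence leaves choices open. It counts headaches rather than days, while the secondary outcomes beside it are partly worded in days and include the duration of individual headaches. The baseline log can run longer than four weeks. Outcome visits can move by two weeks, and if log blocks moved with them, an early first visit would draw in titration days. No rule covers missed log days after randomisation.

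If these choices were really free, one set of logs could yield several primary datasets. A raw count from a block cut short by dropout would be low for a mechanical reason and would look like improvement. Because Section 5.7 unblinds participants one at a time and Section 5.6 starts with graphs by arm, a choice made late could be made with knowledge of allocation.

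**Working it through.** **1. The plan's own figures.** Inputs from Section 5.6 (Sample Size): 74 and 37 completers, effect size 0.57, two-sided 5%, two-sample t-test. Degrees of freedom are 74 + 37 − 2 = 109. The noncentrality is 0.57 × √(74 × 37 / 111) = 0.57 × 4.967 = 2.83, which gives power of 80.1% (stated: 80%). Dropout: 111 / 0.70 = 158.6 (stated: 160). Screen failure: 160 / 0.70 = 228.6 (stated: 228). All reproduce to rounding. The standard deviation of 5 to 6 is in days per month, so the detectable difference is 0.57 × 5 = 2.85 to 0.57 × 6 = 3.42 days. A day count therefore needs no new sample size.

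**2. Unit.** The log as described has one maximum severity per day and no field for counting separate headaches. The sample size for this outcome, and its comparison of entry criteria with earlier trials, are both in days per month. The available count is days with severity 2 or 3. The one pointer the other way, individual headache duration, is a secondary outcome.

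**3. Baseline window.** The Abstract splits the five weeks into four of headache screening and one of sleep monitoring, and 4 + 1 = 5 matches Section 5.1. Using every pre-drug log day would give 28 + 7 = 35 to 28 + 14 = 42 days. Unscaled, 8 days per 28 would then become 8 × 35/28 = 10 to 8 × 42/28 = 12. But neither 35 nor 42 days is a 4-week measure. The 28-day screening log is the reading that fits Sections 5.5 and 5.6 together.

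**4. Follow-up windows.** Visits fall nominally on steady-dose days 28, 56 and 84, each ±14 days. A 28-day look-back from a first visit on day 14 would take 14 of its 28 days (50%) from titration. A count between successive visits could span 28 − 28 = 0 to 28 + 28 = 56 days. Neither rule appears in the document. The 14-day allowance is for rating visits, whereas the log is filled in daily on a calendar form, so its dates do not depend on when the visit takes place. Days 1–28, 29–56 and 57–84 give exactly 28 days each.

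**5. Unlogged days.** The screening minimum is 0.80 × 28 = 22.4, so 23 days, leaving up to 5 unlogged. Suppose 80% logging and no scaling. A count of 8 (the entry minimum) loses 8 × 0.20 = 1.6 days, and 12.4 (the mean in the open-label series, Table 1) loses 12.4 × 0.20 = 2.5. If both arms log equally at follow-up, the loss shrinks a true difference by the same fifth and creates none. A spurious difference needs unequal logging: an assumed 10-point gap gives 8 × 0.10 = 0.8 to 12.4 × 0.10 = 1.2 days. Scaling to 28 days removes it if unlogged days resemble logged ones. The document gives no post-randomisation logging rates.

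**6. Partial blocks.** Dropout of 30% is 0.30 × 160 = 48 participants. That is an upper limit on those leaving with a partly logged steady-dose block, since some leave during titration.

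**7. Eligibility against outcome.** A treated mild day counts only for entry; an untreated moderate day under 4 hours counts only in the outcome. A participant could enter on 8 treated mild days with a primary baseline of 0. Entry is settled before randomisation, so this costs room to improve, not a fair comparison.

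**The case for a change.** The best case for acting is that a primary outcome should leave nothing to inference, and that a few written words cost almost nothing. The unit is never stated, although the neighbouring secondary outcomes do say days. The statement in Section 5.6 that mixed models accommodate missing values concerns missing model observations; it does not say how to build a 4-week count from an incomplete log. Section 5.7 wants early-termination measures in the intent-to-treat analysis, which makes partial blocks likely. Rolling unblinding then makes it preferable to settle the rules before anyone compares arms.

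Most of this stands as description: the unit is inferred, the choice of calendar blocks is inferred, and the unlogged-day rule is absent. What does not stand is the step from there to a defective endpoint. The extreme windows and the truncated raw count come from rules the plan never states. Logs are reviewed at every visit and phone check, Section 5.5 sets out steps to limit missing data, and Section 5.6 compares the rate and timing of dropout by arm, with multiple imputation as an alternative. No passage gives the derivation of the outcome to someone who knows the allocation. A logging cut-off would carry its own cost, because setting sparse blocks to missing discards early-termination log data that Section 5.7 wants kept.

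**Conclusion.** No change is called for. The document points to a count of days with maximum severity moderate or severe, in 4-week blocks closing at steady-dose weeks 4, 8 and 12, with the four-week screening log as baseline. That count gives a valid randomised comparison. The difference from the eligibility headache day is not an error, since an entry rule need not equal the endpoint.

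The real gap is the treatment of unlogged days after randomisation, together with a literal statement of unit and calendar blocks. This is missing detail that analysts would ordinarily settle when deriving the outcome. Power of 80.1% and the figures 111, 160 and 228 are unaffected. The 0.8 to 1.2 day shift needs both an unscaled count and an assumed 10-point logging gap between arms, and the document supports neither. The conclusion rests on the log form matching its description in Section 5.5, and on the derivation being made without regard to treatment arm.

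### The primary model uses one 4-week baseline measure although 35 to 42 pre-dose days are logged, so 7 to 14 days of baseline data go unused

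*Combined protocol and SAP*

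**What the plan says.** Section 5.6 (Statistical Analysis) fits a linear mixed effects model to the primary outcome. "The response (dependent) variable will be 4-week frequency of moderate or severe HAs", and the number and timing of measures is given as "We will have 4-week measures at four times during the course of the study: at Baseline", followed by three during the steady-dose period. The section also promises confidence intervals for change from baseline within each group.

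Section 5.5 (Screening Period) describes the logging. "At the end of 4 weeks of HA log keeping, the HA log will be reviewed at the Final Screening Visit", and "Eligibility criteria include 8 or more HA days in the 4-week period of log keeping". The Baseline Visit comes next, "which will optimally occur 7 days later, but not more than 14 days later". In the interim, participants "continue keeping the HA log and will undergo baseline sleep/activity monitoring with 7 days of actigraphy". The screening log has two uses: to confirm eligibility and "to provide baseline data that will be used for comparison with data from the Steady-Dose Period". Under Titration Period, study drug starts on the evening of the Baseline Visit.

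The sections differ on where the interim week belongs. Section 5.5 (Screening Period) puts it between the Preliminary Screening Period and the Baseline Visit, and the Abstract (Study Design) lists a 4-week headache screening period separately from a 1-week sleep monitoring period. Section 5.1 counts it in, "including a 5-week Preliminary Screening Period during which the participant will keep a HA log". The sleep diary entry in Section 5.5 (Description of Study Measures) also places the pre-treatment diary week within screening.

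**The concern.** The primary question is about change from baseline. In the planned model the baseline count is one of the responses, so its day-to-day noise enters the treatment-by-week contrast. The protocol collects a longer pre-dose record than the model uses, and the extra days cost nothing more to obtain.

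The second issue is selection. Participants enter because their 4-week log reached 8 headache days. Some reach it in a month that was high by chance, and their later counts would fall without treatment. If the baseline is that same log, the fall is built into the within-group changes that Section 5.6 will report. The interim days qualified nobody, so they are free of this effect.

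Finally, the 28 days are not named. Section 5.7 breaks the blind for each participant on exit, before database lock, so the baseline is better fixed in advance than settled at analysis.

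**Working it through.** **Inputs from the documents.** Eligibility log 28 days; interim 7 days (optimal) to 14 days (maximum); completers 74 and 37; effect size 0.57; two-sided 5% level; SD of change 5 to 6 days (Sections 5.5 and 5.6).

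**Assumed, because the documents give no day-level variance.** Days independent; daily headache probability p from 0.3 to 0.6; Final Screening Visit on day 28.

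**1. The plan's own figure.** A noncentral two-sample t-test with 74 and 37 completers at d = 0.57 gives power of 80.1%, matching the stated 80%.

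**2. Pre-dose days.** 28 + 7 = 35 and 28 + 14 = 42. A 28-day measure leaves 35 − 28 = 7 to 42 − 28 = 14 days unused.

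**3. Share of the variance of change due to day-to-day noise.** The noise in one 28-day count is 28p(1 − p): 5.88 at p = 0.30, 7.00 at p = 0.50 and 6.72 at p = 0.60. A change score holds two such counts, so the share is 2 × noise / SD².
- Lowest: 2 × 5.88 / 36 = 0.33.
- Highest: 2 × 7.00 / 25 = 0.56.

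**4. Effect of a D-day baseline scaled to 28 days.** Only the baseline half of the noise shrinks, by 28/D. The variance of change is multiplied by v = 1 − share × 0.5 × (1 − 28/D), and the effective effect size is 0.57/√v.

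| Baseline days | Share | v | Effective d | Power |
|---|---|---|---|---|
| 28 | any | 1 | 0.570 | 80.1% |
| 35 | 0.33 | 0.967 | 0.580 | 81.4% |
| 35 | 0.56 | 0.944 | 0.587 | 82.3% |
| 42 | 0.33 | 0.946 | 0.586 | 82.3% |
| 42 | 0.56 | 0.907 | 0.599 | 83.8% |

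The variance falls by about 3 to 5.5% with 35 days and 5.5 to 9% with 42. In completers, 111/v − 111 is about 4 to 7 and 6 to 11 respectively.

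**5. Upper limit.** If all the variance of change were day-level noise (share = 1), v would be 0.90 and 0.833, and power 84.1% and 86.7%.

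**6. Regression to the mean.** A beta-binomial simulation applied the threshold of 8 in 28, with an assumed pre-selection mean of 8 to 15 days per 28 and between-person SD of 3 to 5. It treats threshold and outcome as the same variable. Mean baseline exceeded the true mean of those selected by 0.1 to 1.1 days when the first 28 days were used. The excess sits only in the selected days, so pooling all days multiplies it by 28/D:
- 35 days: 1.1 × 0.80 = 0.88, a range of 0.1 to 0.9.
- 42 days: 1.1 × 0.667 = 0.73, a range of 0.1 to 0.7.

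**The case against.** The strongest reply is that the plan never says that it discards the selection-free days. Section 5.6 does not name its 28 days. Section 5.1 and the sleep diary entry can be read as making the interim week part of the screening log. If the window were the 28 days ending at the Baseline Visit, the interim days would form 7/28 = 25% to 14/28 = 50% of it, and early screening days would drop out instead. This stands. A reader might infer that the plan expressly excludes the unselected days; the documents support that only as the most natural reading. Some 7 to 14 logged days are unused on either reading.

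A second reply is that matched 28-day windows are a legitimate choice, and that a last-28-days window would cut the selection excess slightly more (0.1 to 0.8 days with a 7-day interim, 0.1 to 0.6 with 14) while keeping lengths equal. That is fair on selection alone, but it still gives up 7 to 14 days of precision. Replacing the 4-week log by the interim days alone would be worse: power in a change-score test falls to about 43 to 73%, taking day noise at p = 0.44 or as all of the variance of change. The interim days can only supplement the log.

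A third reply is that the magnitude rests on assumptions. It does. The figures are for an unadjusted change score with independent days. Between-person spread in p would lower the noise, and short runs of headache days would raise it. The 42-day figures need the longest permitted interval. Section 5.5 ties its 80% completeness check to the 4-week log and states none for the interim days.

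**Conclusion.** The point holds as a low-priority improvement. The primary baseline uses 28 of 35 to 42 logged pre-dose days, and the plan does not say which 28. Using all of them would lower the variance of an unadjusted change score by about 3 to 5.5% at the usual 7-day interval, or 5.5 to 9% at the 14-day maximum, worth roughly 1 to 4 points of power. This depends on the assumed daily probability and independence of days; the gain in the planned mixed model may differ.

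A reader might also infer that selection at the threshold biases the treatment comparison. It does not. Selection happens before dosing under one rule for both arms, so the excess cancels in expectation from the between-arm difference. It affects only the within-group changes, where pooling all days reduces it without removing it. Its size is uncertain too, because the threshold counts headache days, including treated headaches of any severity, while the modelled outcome is moderate or severe headaches.

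**What to change.** In Section 5.6, define the baseline of the primary outcome as the rate per 28 logged days over all days from the start of the log to the day before the first dose. For a rescreened participant, start from the log that qualified them. Put the follow-up windows on the same per-28-logged-days scale, so that incomplete logs are treated alike before and after dosing. Leave the eligibility count on the first 4 weeks.

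Reconcile the Abstract, Section 5.1 and the two parts of Section 5.5 on whether the interim week belongs to the Preliminary Screening Period.

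The cost is a short addition to the analysis section and a wording correction, with no new data, visits or eligibility change. The one small drawback is that the baseline window varies between participants (35 to 42 days) and is longer than the 28-day follow-up windows; the rate scale handles the difference in length, though not the slight difference in precision.

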#### 5.6 Data Analysis

**Sample Size:** Our estimate of required sample size for the primary outcome is based on previous studies of chronic migraine HA, which reported standard deviations for change from baseline at 16 weeks in number of migraine days/month on the order of 5-6 days for both placebo and active drug groups, and a difference in change from baseline at 16 weeks in mean number of chronic migraine HA days/month between treatment groups of about 4 days (i.e., an effect size of about 0.67). An inclusion criterion for these studies was a minimum of 15 HA days/month, whereas the corresponding inclusion criterion for our proposed study is a minimum of 8 HA days/month. We therefore may see a smaller effect size. A trial with 111 completers (74 in the prazosin group, and 37 in the placebo group) yields 80% power to detect an effect size of 0.57 for a difference in change from baseline based on a standard two-sample t-test using a two-sided 5% Type I error level. Because we will be using linear mixed effects models to analyze this outcome, our power should be greater than 80% to detect an effect size of 0.57.

To arrive at the required number of participants to randomize, we are assuming a 30% dropout rate during the Titration and Steady-Dose Periods, based on the experience of Study Consultant [name] in other HA trials in the active-duty SM population. This dropout rate is due mainly to service-related events, such as reassignment or deployment, rather than to adverse drug effects. With a 30% dropout rate, we will need to randomize 160 participants who have met all eligibility criteria. Conservatively assuming a screen-fail rate of approximately 30% based on the Pre-Treatment Screening (e.g., meeting inclusion criteria for HA frequency/severity, adequate compliance with log keeping, voluntary study withdrawal, etc.), 228 potential participants will need to be recruited and enrolled to provide sufficient participants randomized for completion of the study.

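### The blinded headache logs from the 5-7 week titration enter no listed analysis, so the primary model cannot use the recorded course of participants who leave before the first steady-dose block closes

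*Combined protocol and SAP*

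**What the plan says.** Participants are randomized before the Baseline Visit and start study drug that evening (section 5.5). On the log, section 5.5 says that "they will continue keeping the HA log for the remainder of the study phases, including the Titration and Steady-Dose Periods". The same paragraph, however, names only the steady-dose data as the comparison with baseline.

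The primary mixed model in section 5.6 has four-week measures "at Baseline, and at three different time points post-randomization (after 4, 8, and 12 weeks of steady-dose study drug". The log-based secondary outcomes use the same four times. The test is the treatment-by-week interaction, and the analysis is stated to be intent-to-treat.

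Four other provisions bear on early leavers:
- Section 5.7 allows discontinuation for intolerable worsening of headaches and requires it when a new scheduled headache prophylactic is started. Sections 5.5 and 5.7 end participation if the lowest dose is not tolerated.
- Sections 5.5 and 5.7 provide for an attempted early-termination visit with the week-12 procedures, so that its measures can enter the intent-to-treat analyses. No text says which model time point this record takes or how a partial four-week block is counted.
- Section 5.6 will compare the rate and timing of dropout by arm, and explore multiple imputation if the pattern is disparate.
- On the amount of dropout, section 5.6 says "we are assuming a 30% dropout rate during the Titration and Steady-Dose Periods", and attributes it mainly to service-related events.

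**The concern.** Reaching the first analysed post-baseline block is itself a post-randomization event that treatment may influence. A participant who leaves earlier stays in the mixed model through the baseline value but adds almost nothing to the treatment-by-week contrast. The model in effect predicts that person's steady-dose course from baseline and covariates, using those who stayed.

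That prediction is sound if exit is unrelated to headache course, given baseline and covariates. The protocol's own exit rules make this uncertain, because worsening headache and intolerance are both grounds for leaving. During titration, worsening would show in the daily log, which the listed model never sees. If exit follows the early course and does so differently by arm, the estimate can be biased even though data that could reduce the bias were collected. The titration logs are also written under blind, whereas section 5.7 breaks the blind on the day of discontinuation, so termination-visit measures may be taken after unblinding.

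**Working it through.** **1. The plan's own figure.** Section 5.6 states "A trial with 111 completers (74 in the prazosin group, and 37 in the placebo group" and that this "yields 80% power to detect an effect size of 0.57", "based on a standard two-sample t-test using a two-sided 5% Type I error level". Allocation is 2:1 (section 5.1).
- Noncentrality = 0.57 / sqrt(1/37 + 1/74) = 0.57 / 0.2013 = 2.83.
- Normal approximation: Phi(2.83 - 1.96) = 80.8%. Noncentral t on 109 df: 80.1%.
- 111 / 0.70 = 158.6, so 159 randomized; the plan has 160, and 160 x 0.70 = 112.

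The sample size reproduces.

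**2. What the listed time points leave out.** On-drug logging lasts 5 + 12 = 17 to 7 + 12 = 19 weeks. Titration is 5/17 = 29% to 7/19 = 37% of it. The first steady-dose block closes at 5 + 4 = 9 to 7 + 4 = 11 weeks.

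**3. How many could leave before that.** Total expected dropout is 0.30 x 160 = 48. Its timing is not given, so the possible number is 0 to 48. Assuming a constant hazard, the proportion remaining at week w of T is S(w) = 0.70^(w/T), and the number lost is 160 x (1 - S).

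| Lost by | 5-week titration (T = 17) | 7-week titration (T = 19) |
|---|---|---|
| Week 4 of titration | 12.9 | 11.6 |
| End of titration | 15.9 | 19.7 |
| First steady-dose block closes | 27.5 | 29.9 |
| Share of the 48 lost by then | 57% | 62% |

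Of those lost before the first block closes, 27.5 - 12.9 = 14.6 to 29.9 - 11.6 = 18.3, or about 15-18, would have been in the trial long enough for a full 28-day titration block. The other 12-13 would have at most a partial one.

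**4. Power.** With 28-30 lost, 130-132 remain, and nominal power at 0.57 is still about 87%. The plan was sized on completers, so these losses do not take power below plan.

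**5. Possible bias: two illustrations on assumed inputs.**

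*A. No true effect.* 107:53 randomized, SD 6 days, correlation 0.5 with baseline and 0.7 between titration and steady dose. In the informative rows, exit is likelier with more headache in titration. A negative value favours prazosin.

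| Loss, prazosin / placebo | Mechanism | Bias without titration log (days) | With |
|---|---|---|---|
| 10% / 10% | random | 0.00 | 0.00 |
| 10% / 10% | informative | -0.06 | -0.03 |
| 10% / 5% | informative | -0.07 | 0.05 |
| 20% / 5% | informative | -0.37 | 0.02 |
| 20% / 10% | informative | -0.27 | 0.02 |
| 30% / 10% | informative | -0.59 | -0.01 |

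The sampling SD of the estimate is about 1.05 days.

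*B. True effect -3.4 days.* This is about 0.57 x 6 = 3.42, taking 6 as the upper end of SDs "on the order of 5-6 days for both placebo and active drug groups". Half the effect is present in titration and the correlation is 0.6. Prazosin loss is 17% at random; placebo loss is 11-25% and related to poor change in titration. Without the titration block the estimate is -2.87 to -3.28, an attenuation of (3.40 - 3.28)/3.40 = 4% to (3.40 - 2.87)/3.40 = 16%. With it, the estimate is -3.39 to -3.42.

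A errs towards prazosin and B against it. In both, informative exit was made to depend on the titration course, so conditioning on that course restores the truth largely by construction. They show the mechanism, not an expected size.

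**The case against.** A reader might infer that early leavers have no post-baseline headache data at all, or that the intent-to-treat claim is breached. The documents support neither. A termination visit is attempted, with the end-of-study measures (headache log review, HIT-6 and MIDAS among them) intended for the intent-to-treat analyses, and every randomized participant stays in the model. What stands is narrower: the visit happens only where possible, and its record has no assigned time point. A titration leaver has no steady-dose log to place, so the record is either unused or entered as something it is not.

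A reader might also infer that substantial bias is likely. Section 5.6 expects mainly service-related exits, and section 5.1 reports about 5% stopping prazosin for side effects, roughly 5 of 107 on prazosin. Doses can be held, reduced or re-challenged, with up to two extra titration visits. If exits are unrelated to headache, or depend on the early course about equally in both arms, the bias is zero or close to it. This objection stands as to size.

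The missing-data plan is a partial answer. Differential dropout is its trigger, but imputation is only to be explored, and the titration logs are not named as predictors.

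Finally, a steady-dose endpoint is a legitimate choice, and the titration block would not rescue everyone. Some leavers have little log, the early days are at low doses, and a paper log may not come back from someone who leaves abruptly. All of this stands and limits the benefit.

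**Conclusion.** The point holds as a cheap improvement, not as an error in the plan. The listed primary model omits 29-37% of the on-drug log weeks and gives participants lost before 9-11 weeks no listed post-baseline primary observation. The figure of about 28-30 of 160 rests on the plan's 30% dropout and an assumed constant hazard; the documents allow anything from 0 to 48. In the illustrations the bias ranges from zero to about 0.6 days towards prazosin (A), or up to 16% attenuation (B). Those sizes depend on assumed correlations and arm-specific informative loss, and neither direction can be ruled out beforehand. What does not depend on them is that using the blinded titration logs makes missing-at-random more plausible, from data the trial already collects.

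**What to change.** In section 5.6:
1. Add a titration-period log block to the primary mixed model as a post-randomization repeated measure, for example study-drug days 1-28. Derive it as headache days per logged day x 28, keep partial blocks, and treat week as a categorical factor.
2. State that the deciding test is the treatment difference in change from baseline in the steady-dose period, not the overall interaction, which would now include the titration level.
3. Place logs from early leavers in the period in which they were recorded.
4. Name the titration block as a predictor in any multiple imputation.
5. Do the same for the log-based secondary outcomes.

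The cost is analysis-plan wording and one derived time point, with no new data, visits or participants. The downsides are one more time level and its interaction to estimate, a test that must be worded as a specific contrast, and some early leavers who will still have little or no titration log.
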